1.3 Number of subjects

The study will randomise approximately 400 patients in the ITT population and approximately 375 patients in the mITT population. Patients who received prior concurrent chemoradiation (cCRT) or sequential chemoradiation (sCRT) and have not progressed following definitive chemoradiation therapy will be randomised in a 2:1 ratio to receive durvalumab and placebo.

Randomisation will be stratified by the level of PD-L1 expression (PD-L1 <1% or PD-L1 ≥1%) and prior therapy (cCRT or sCRT).

The number of patients with sensitizing epidermal growth factor receptor (EGFR) mutation or anaplastic lymphoma kinase (ALK) rearrangement randomised will be capped at approximately 7% of the total number of patients randomised. In order to reflect global clinical practice, study will recruit at least 60% of patients who received prior cCRT. The majority of patients will be recruited in China.

Eligible patients will be in complete response (CR), partial response (PR), or have stable disease (SD) following definitive, platinum-based, cCRT or sCRT.

The primary objective of this study is to assess the efficacy of durvalumab compared with placebo in terms of PFS per RECIST 1.1 as assessed by BICR in the mITT population. The key secondary endpoint (i.e., included in the multiple testing procedure) is OS (mITT).

The primary PFS (mITT) analysis data cut-off (DCO) will occur when whichever of the following conditions have been met first:

- Reaching approximately [CCI] BICR progression-free survival events across the durvalumab and placebo treatment arms (approximately [CCI] maturity) in the mITT population

OR

- Approximately [CCI] months follow-up from last patient randomized to the study.

If the true PFS HR is [CCI] with an estimated [CCI] BICR PFS events in the mITT, the study will provide at least [CCI] power to demonstrate a statistically significant difference for PFS with [CCI] this translates to approximately a [CCI]-month benefit in median PFS over [CCI] months on placebo. The smallest treatment difference that would be statistically significant is a HR of [CCI]. A recruitment period of approximately [CCI] months and a follow-up period of [CCI] months are expected for the PFS (mITT) final analysis.

The overall alpha level for the statistical testing of the secondary key endpoint OS ([CCI]) for durvalumab versus placebo will be [CCI]. The final planned OS analysis DCO will occur when reaching approximately [CCI] death events ([CCI] maturity) or approximately [CCI] months follow-up from the last participant randomization in the [CCI], whichever occurs first. If the true OS hazard ratio (HR) is [CCI] with an estimated [CCI] OS events, this study will provide [CCI] power to demonstrate a statistically significant difference for OS, assuming a [CCI] 2-sided significance level (with overall 2-sided alpha for OS as [CCI]); this translates to an [CCI]-month benefit in median OS over [CCI] months on placebo. The smallest treatment difference that would be statistically significant is a HR of [CCI]. Up to two interim analyses for OS will be conducted: 1) at the same time as primary PFS analysis and 2) at approximately [CCI] months after the OS first interim analysis, with approximately [CCI] and [CCI] of the target events respectively. If the expected DCO for OS final analysis is within [CCI] months after the OS first interim analysis, the OS second interim analysis may be removed. A recruitment period of approximately [CCI] months and a follow-up period of [CCI] months are expected for the final analysis of the OS endpoint.

2 ANALYSIS SETS

2.1 Definition of analysis sets

Summaries of the analysis sets for each outcome variable are provided in [Table 1](#).

Table 1 Summary of outcome variables and analysis populations

Outcome variable	Populations
Efficacy data	
PFS	mITT and ITT ^a
OS, OS24, PFS12, PFS18, PFS2, PRO endpoints, TTDM, ORR* (with/without confirmed response) and DoR* (with/without confirmed response)	mITT and ITT ^a
Study population/demography	
Demography	mITT and ITT ^a
Prior anti-cancer therapy	mITT and ITT ^a
Protocol deviations	mITT and ITT ^a
Medical and surgical history	mITT and ITT ^a
Patient characteristics	mITT and ITT ^a
Concomitant medications	mITT and ITT ^a
PK/ADA data	
PK data	PK analysis set
ADA	ADA analysis set
Safety data	
Exposure	Safety analysis set
Adverse events	Safety analysis set
Laboratory measurements	Safety analysis set
Vital Signs	Safety analysis set

^a ITT is the secondary population for efficacy analysis.

DoR Duration of response; ITT Intent-to-treat; mITT Modified Intent-to-treat; ORR Objective response rate; OS overall survival; OS24 Proportion of patients alive at 24 months from randomisation; PFS Progression-free survival; PFS2 Time from randomisation to second progression; PFS12 Proportion of patients alive and progression-free at 12 months from randomisation; PFS18 Proportion of patients alive and progression-free at 18 months from randomisation; PK Pharmacokinetic; PRO Patient-reported outcomes; TTDM Time to death or distant metastasis.

* Patients who are evaluable for the analysis of ORR are those with measurable disease at baseline. Patients who are evaluable for the analysis of DoR are those who responded in the ORR analysis.

2.1.1 Intent-to-treat (ITT) set

The ITT set will include all randomised patients. The ITT set will be used as secondary population for efficacy analyses (including PROs). Treatment arms will be compared based on randomised study treatment, regardless of the treatment actually received. Patients who were

randomised but did not subsequently go on to receive study treatment will be included in the analysis in the treatment arm to which they were randomised.

ITT set with measurable disease at baseline

A subset of the ITT set including only those patients with measurable disease at baseline will be applied to all ORR and some BoR endpoint summaries.

China ITT set

A subset of the ITT set including only those patients from sites located in mainland China.

The other country/region ITT set may be planned since the analysis based on country/region ITT set may be performed per the request from local health authority.

2.1.2 Modified intent-to-treat set

The mITT set will include all randomised patients in the ITT set who are without sensitizing EGFR mutations or ALK rearrangements. Unless otherwise specified, the mITT set will be used as primary population for all efficacy analyses (including PROs). Treatment arms will be compared based on randomised study treatment, regardless of the treatment actually received.

Information on EGFR/ALK status will be based on eCRF data. If a patient has EGFR/ALK valid results from both local and central laboratories, then results from central laboratories will be used.

China mITT set

A subset of the mITT set including only those patients without sensitizing EGFR mutations or ALK rearrangements from sites located in mainland China.

The other country/region mITT set may be planned since the analysis based on country/region mITT set may be performed per the request from local health authority.

2.1.3 Safety analysis set

The safety analysis set will consist of all patients who received at least 1 dose (full or partial) of study treatment (durvalumab or placebo). Safety data will not be formally analysed but summarised using the safety analysis set according to the treatment received; that is, erroneously treated patients (e.g., those randomised to treatment A but actually given treatment B) will be summarised according to the treatment they actually received. If a patient receives any amount of durvalumab, they will be summarised in the durvalumab arm.

China safety analysis set

A subset of the safety analysis set including all patients recruited from sites located in mainland China who received at least 1 dose (full or partial) of study treatment (durvalumab or placebo).

The other country/region safety analysis set may be planned since the analysis based on country/region safety analysis set may be performed per the request from local health authority.

2.1.4 PK analysis set

All patients who receive at least 1 dose of durvalumab per the CSP for whom any post-dose data are available and who do not violate or deviate from the CSP in ways that would significantly affect the PK analyses will be included in the PK analysis set. The population will be defined by the Study Physician, Pharmacokineticist, and Statistician prior to any analyses being performed.

China PK analysis set

A subset of the PK analysis set including all patients recruited from sites located in mainland China who receive at least 1 dose of durvalumab per the CSP for whom any post-dose data are available and who do not violate or deviate from the CSP in ways that would significantly affect the PK analyses.

2.1.5 ADA analysis set

All patients who have non-missing baseline ADA and at least 1 non-missing post-baseline ADA result will be included in the ADA analysis set.

China ADA analysis set

A subset of the ADA analysis set including all patients recruited from sites located in mainland China who have non-missing baseline ADA and at least 1 non-missing post-baseline ADA result.

2.2 Violations and deviations

The following general categories will be considered important deviations and will be listed and discussed in the clinical study report (CSR) as appropriate for the study:

- Deviation a: Patients randomised but who did not receive durvalumab/matching placebo

- Deviation b: Patients who deviate from the following key entry criteria in CSP:
 - a) Part I inclusion criteria: 2, 6; Part II inclusion criteria: 2, 4, 5, 6.
 - b) Exclusion criteria: 7, 11.
- Deviation c: Baseline RECIST 1.1 scan > 42 days before randomisation.
- Deviation d: No baseline RECIST 1.1 assessment on or before date of randomisation or baseline RECIST assessment is performed before the completion of Chemoradiation therapy.
- Deviation e: Patients randomised who received treatment other than that to which they were randomised.
- Deviation f: Received prohibited concomitant medication.
- Deviation g: discontinuation criteria for study product met but patients not withdrawn from study treatment.

Prior to database lock (DBL), medications will be reviewed by a physician on a regular basis, and a decision made by the study team, in order to classify medications that are ‘prohibited’ from permitted use during the study.

The categorisation of these as important deviations is not automatic and will depend on duration and the perceived effect on efficacy.

Patients who receive the wrong treatment at any time will be included in the safety analysis set as described in [Section 2.1](#). During the study, decisions on how to handle errors in treatment dispensing (with regards to continuation/discontinuation of study treatment or, if applicable, analytically) will be made on an individual basis with written instruction from the study team leader and/or statistician.

The important protocol deviations will be listed and summarised by randomised treatment group. Deviation ‘a’ will lead to exclusion from the safety analysis set. None of the other deviations will lead to patients being excluded from the analysis sets described in [Section 2.1](#) (except for the PK analysis set, if the deviation is considered to significantly impact upon PK, and except for the ADA analysis set). A per protocol analysis excluding patients with specific important protocol deviations is not planned; however, a ‘deviation bias’ sensitivity analysis may be performed excluding patients with deviations that may affect the efficacy of the trial therapy if > 10% of patients in either treatment group:

- Did not have the intended disease or indication or
- Did not receive any randomised therapy.

The need for such a sensitivity analysis will be determined following review of the protocol deviations ahead of database lock and will be documented prior to the primary analysis being conducted.

Protocol deviations, along with other study deviations, will be noted by the monitors (on the electronic case report form [eCRF] for inclusion/exclusion criteria) throughout the study period and these will be reviewed by the study team to determine whether they are to be classified as important deviations and to be summarised/listed in the CSR. In addition to the programmatic determination of deviations above, other study deviations captured from the electronic case report form (eCRF) module for inclusion/exclusion criteria will be tabulated and listed. Any other deviations from monitoring notes or reports will be reported in an appendix to the CSR.

In addition, the number and percentage of patients with at least one COVID-19 pandemic related important protocol deviations will be summarized. A listing for patients with reported issues due to COVID-19 pandemic will be provided, as reported by the sites.

3 PRIMARY AND SECONDARY VARIABLES

3.1 Derivation of RECIST 1.1 visit responses

For all patients, the RECIST 1.1 tumour response data will be used to determine each patient's visit response according to RECIST 1.1. It will also be used to determine if, and when, a patient has progressed and their best objective response (BoR) to study treatment.

Part II screening/baseline radiological tumour assessments are to be performed no more than 28 days before the start of randomisation and ideally as close as possible to and prior to the start of study treatment. Tumour assessments are then performed after randomisation every 8 weeks \pm 1 week for the first 48 weeks and then every 12 weeks \pm 1 week thereafter until RECIST 1.1-defined radiological progression. A follow-up scan is to be collected after the initial RECIST 1.1-defined radiological PD, no less than 4 weeks after the prior assessment of PD and no later than the next regularly scheduled imaging visit and this follow-up scan is evaluated using the Confirmation of Radiological Progression criteria outlined in CSP Appendix E. If the subsequent scan confirms the immediate prior radiological PD, no additional scans are required; however, if the subsequent scan does not confirm the immediate prior radiological PD, scanning should continue until the next RECIST 1.1-defined radiological PD, which in turn will require a subsequent scan evaluated using the Confirmation of Radiological Progression criteria outlined in CSP Appendix E.

If an unscheduled assessment is performed, and the patient has not progressed, every attempt should be made to perform the subsequent assessments at their scheduled visits. This schedule is to be followed to minimise any unintentional bias caused by some patients being assessed at a different frequency than other patients.

From the investigator's review of the imaging scans, the RECIST 1.1 tumour response data will be used to determine each patient's visit response according to RECIST 1.1. At each visit, patients will be programmatically assigned a RECIST 1.1 visit response of CR, PR, SD or progression of disease (PD), using the information from target lesions (TLs), non-target lesions (NTLs) and new lesions and depending on the status of their disease compared with baseline and previous assessments. If a patient has had a tumour assessment that cannot be evaluated, then the patient will be assigned a visit response of not evaluable (NE) (unless there is evidence of progression in which case the response will be assigned as PD).

RECIST 1.1 outcomes (i.e., PFS and ORR etc.) will be calculated programmatically for the BICR and site investigator data from overall visit responses.

The above derivations will be programmed for the BICR based upon RECIST 1.1 assessments. Measurements from the reviewer selected by the adjudicator will be used when adjudication for overall visit response has occurred, but in the case where no adjudication was required, the measurements from the reviewer who reviewed the baseline scan first will be used for this analysis. Note: this window rule will be applicable to other secondary efficacy outcome endpoints that involve RECIST 1.1 scans.

3.1.1 Site investigator assessments using RECIST 1.1

3.1.1.1 Target lesions

Measurable disease is defined as having at least one measurable lesion which is ≥ 10 mm in the longest diameter (LD), (except lymph nodes which must have short axis ≥ 15 mm) with computed tomography (CT) or magnetic resonance imaging (MRI) and which is suitable for accurate repeated measurements. A patient can have a maximum of five measurable lesions recorded at baseline (with a maximum of two measurable lesions per organ), representative of all lesions involved and suitable for accurate repeated measurement, and these are referred to as TLs. If more than one baseline scan is recorded, then measurements from the one that is closest and prior to randomisation will be used to define the baseline sum of TLs. It may be the case that, on occasion, the largest lesion does not lend itself to reproducible measurement and in this circumstance, the next largest lesion, which can be measured reproducibly, should be selected.

Details of TL visit response categories are provided in [Table 2](#). See CSP Appendix E for further details on how to handle special cases of TLs.

All other lesions (or sites of disease) not recorded as TL should be identified as NTLs at baseline. Measurements are not required for these lesions, but their status should be followed at subsequent visits.

Note: For patients who do not have measurable disease at entry (i.e. no TLs) but have non-measurable disease, evaluation of overall visit responses will be based on the overall NTL assessment and the absence/presence of new lesions (see [Section 3.1.1.2](#) for further details). If a patient does not have measurable disease at baseline, then the TL visit response will be not applicable (NA).

Rounding of TL data

For calculation of progressive disease (PD) and PR for TLs percentage changes from baseline and previous minimum should be rounded to 1 decimal place (d.p.) before assigning a TL response. For example, 19.95% should be rounded to 20.0% but 19.94% should be rounded to 19.9%

Table 2 TL Visit Responses

Visit Responses	Description
Complete response (CR)	Disappearance of all TLs since baseline. Any pathological lymph nodes selected as TLs must have a reduction in short axis to <10 mm.
Partial response (PR)	At least a 30% decrease in the sum of the diameters of TLs, taking as reference the baseline sum of diameters as long as criteria for PD are not met.
Stable disease (SD)	Neither sufficient shrinkage to qualify for PR nor sufficient increase to qualify for PD.
Progression of disease (PD)	A $\geq 20\%$ increase in the sum of diameters of TLs and an absolute increase of ≥ 5 mm, taking as reference the smallest sum of diameters since treatment started including the baseline sum of diameters.
Not evaluable (NE)	Only relevant if any of the TLs at follow-up were not assessed or not evaluable or had a lesion intervention at this visit; and scaling up could not be performed for lesions with interventions. Note: If the sum of diameters meets the PD criteria, progressive disease overrides NE as a TL response.
Not applicable (NA)	No TLs are recorded at baseline.

Missing TL data

For a visit to be evaluable then all TL measurements should be recorded. However, a visit response of PD should still be assigned if any of the following occurred:

- A new lesion is recorded
- An NTL visit response of PD is recorded
- The sum of available TLs is sufficiently increased to result in a 20% increase, and an absolute increase of ≥ 5 mm, from nadir even assuming the non-recorded TLs have disappeared.

Note: the nadir can only be taken from assessments where all the TLs had an LD recorded.

If there is at least one TL measurement missing and a visit response of PD cannot be assigned, the visit response is NE.

If all TL measurements are missing then the TL visit response is NE. Overall visit response will also be NE, unless there is a progression of non-TLs or new lesions, in which case the response will be PD.

Lymph nodes

For lymph nodes, if the size reduces to < 10 mm then these are considered non-pathological. However, a size will still be given, and this size should still be used to determine the TL visit response as normal. In the special case where all lymph nodes are < 10 mm and all other TLs are 0 mm then although the sum may be > 0 mm the calculation of TL response should be overwritten as a CR.

TL Visit responses subsequent to CR

A CR response can only be followed by CR, PD or NE. If a CR has occurred, then the following rules at the subsequent visits must be applied:

- Step 1: If all lesions meet the CR criteria (i.e. 0 mm or < 10 mm for lymph nodes) then response will be set to CR irrespective of whether the criteria for PD of TL is also met i.e. if a lymph node LD increases by 20% but remains < 10 mm.
- Step 2: If some lesion measurements are missing but all other lesions meet the CR criteria (i.e. 0 mm or < 10 mm for lymph nodes) then response will be set to NE irrespective of whether, when referencing the sum of TL diameters, the criteria for PD is also met.

- Step 3: If not all lesions meet the CR criteria and the sum of lesions meets the criteria for PD then response will be set to PD
- Step 4: If after steps 1 – 3 a response can still not be determined, the response will be set to remain as CR

TL too big to measure

If a TL becomes too big to measure this should be indicated in the database and a size ('x') above which it cannot be accurately measured should be recorded. If using a value of x in the calculation of TL response would not give an overall visit response of PD, then this will be flagged and reviewed by the study team blinded to treatment assignment. It is expected that a visit response of PD will remain in the vast majority of cases.

TL too small to measure

If a TL becomes too small to measure, then this will be indicated as such on the eCRF and a value of 5 mm will be entered into the database and used in TL calculations.

However, a smaller value may be used if the radiologist has not indicated 'too small to measure' on the eCRF and has entered a smaller value that can be reliably measured. If a TL response results in PD, then this will be reviewed by the study team blinded to treatment assignment.

Irradiated lesions/lesion intervention

Previously irradiated lesions may be considered measurable and selected as target lesions, provided they fulfil the other criteria for measurability (i.e., reproducible measurability). This is because all patients will have received radiation therapy immediately prior to randomised study treatment as part of their standard of care.

Any TL (including lymph nodes), which has had intervention in addition to study treatment during the study (e.g. irradiation / palliative surgery / embolization), should be handled in the following way and once a lesion has had intervention then it should be treated as having intervention for the remainder of the study noting that an intervention will most likely shrink the size of tumours:

- Step 1: the diameters of the TLs (including the lesions that have had intervention) will be summed and the calculation will be performed in the usual manner. If the visit response is PD, this will remain as a valid response category.
- Step 2: If there was no evidence of progression after step 1, treat the lesion diameter (for those lesions with intervention) as missing and scale up as described below. If the

scaling results in a visit response of PD then the patient would be assigned a TL response of PD.

Note: scaling up will only be performed if $\leq 1/3$ of the TL measurements have been set to missing following an intervention. If $> 1/3$ of TL measurements are set to missing, then TL response will be set to NE.

- Step 3: If, after both steps, PD has not been assigned then, if appropriate, the scaled sum of diameters calculated in step 2 should be used, and PR or SD then assigned as the visit response. Patients with intervention are evaluable for CR on the condition that all non-intervened lesions are 0 (or < 10 mm for lymph nodes) and the lesions that have been subject to intervention also have a value of 0 (or < 10 mm for lymph nodes) recorded. If scaling up is not appropriate due to too few non-missing measurements, then the visit response will be set as NE.

At subsequent visits the above steps will be repeated to determine the TL and overall visit response. When calculating the previous minimum (the nadir), lesions with intervention should be treated as missing and scaled up where appropriate (as per step 2 above).

Scaling (applicable only for irradiated lesions/lesion intervention)

If $> 1/3$ of TL measurements are missing (because of intervention) then TL response will be NE, unless the sum of diameters of non-missing TL would result in PD (i.e. if using a value of 0 for missing lesions, the sum of diameters has still increased by 20% or more compared to nadir and the sum of TLs has increased by ≥ 5 mm from nadir).

If $\leq 1/3$ of the TL measurements are missing (because of intervention) then the results will be scaled up based on the sizes at the nadir visit to give an estimated sum of diameters and this will be used in calculations; this is equivalent to comparing the visit sum of diameters of the non-missing lesions to the nadir sum of diameters excluding the lesions with missing measurements.

CR will not be allowed as a TL response for visits where there is missing data. Only PR, SD or PD (or NE) could be assigned as the TL visit response in these cases. However, for visits with $\leq 1/3$ lesion assessments not recorded, the scaled-up sum of TLs diameters will be included when defining the nadir value for the assessment of progression.

[Table 3](#) provides an example of scaling-up. Lesion 5 has received intervention prior to the follow-up visit and has been set to missing. The sum of lesions 1-4 at the follow-up is 26 cm. The sum of the corresponding lesions at the nadir visit is 26.8 cm. Scale up as follows to give an estimated TL sum of 28.4 cm:

$$\frac{26}{26.8} \times 29.3 = 28.4$$

Table 3 Example of scaling-up

Lesion	Longest diameter at baseline visit	Longest diameter at follow-up visit
1	7.2	7.1
2	6.7	6.4
3	4.3	4.0
4	8.6	8.5
5	2.5	Missing
Sum	29.3	26

Lesions that split in two

If a TL splits in two, then the LDs of the split lesions should be summed and reported as the LD for the lesion that split.

Lesions that merge

If two TLs merge, then the LD of the merged lesion should be recorded for one of the TL sizes and the other TL size should be recorded as 0 cm.

Change in method of assessment of TLs

CT and MRI are the only methods of assessment that can be used within this trial, with CT and MRI being the preferred methods. If a change in method of assessment occurs, between CT and MRI this will be considered acceptable and no adjustment within the programming is needed.

Note, if a change in method involves clinical examination (e.g. CT changes to clinical examination or vice versa), any affected lesions should be treated as missing.

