3.2.2 Secondary efficacy outcome endpoints

For analysis purpose and except otherwise specified, subsequent anti-cancer therapies include radiotherapies, except palliative radiotherapies.

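### Two target-lesion rules in SAP 3.1.1.1 give inconsistent Investigator visit responses: CR or NE when a lesion is missing after a CR, and CR or NE when more than one third of lesions have been locally treated

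*SAP*

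**What the plan says.** All of these rules stand in SAP 3.1.1.1, within the section on site Investigator assessments.

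**Missing lesions.** Under Missing TL data, a PD can still be assigned on the available evidence. Otherwise: "If there is at least one TL measurement missing and a visit response of PD cannot be assigned, the visit response is NE". No exception is made for patients who have already had a CR.

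**Visits after a CR.** Four steps apply in turn.
- Step 1 keeps CR if every lesion still meets the CR criteria.
- Step 2 gives NE if some measurements are missing and all the others still meet CR.
- Step 3 gives PD if not all lesions meet CR and the sum meets the PD criteria.
- Step 4 is the fallback: if "a response can still not be determined, the response will be set to remain as CR".

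**Lesions with an intervention** (irradiation, palliative surgery, embolization). Step 2 treats the lesion as missing and scales up the sum. Its note allows scaling only if no more than one third of TL measurements have been set to missing, and gives NE otherwise. The NE row of Table 2 agrees. Step 3 then says "Patients with intervention are evaluable for CR on the condition that all non-intervened lesions are 0" (or below 10 mm for nodes) and that the treated lesions read the same. The Scaling paragraph, whose heading limits it to intervention lesions, repeats the one-third limit and says "CR will not be allowed as a TL response for visits where there is missing data".

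**Subsequent therapy.** SAP 3.2.2 states that "subsequent anti-cancer therapies include radiotherapies, except palliative radiotherapies".

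**The concern.** Read literally, the post-CR steps give the patient whose disease has begun to regrow a better visit response than the patient whose disease has not. The intervention rules give two answers for one set of measurements, depending on which sentence the programmer follows. The SAP states no order of precedence in either case.

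These rules feed the Investigator-based PFS (the ascertainment-bias analysis in SAP 4.2.1), the Investigator ORR sensitivity analysis (SAP 4.2.2.3), the Investigator best objective response, and PFS12 and PFS18 as SAP 3.2.2.5 defines them. The Investigator PFS and ORR are there to check the BICR results, so they should not depend on an unrecorded programming choice.

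**Working it through.** **Inputs.** TL progression needs a rise of at least 20% and at least 5 mm, "taking as reference the smallest sum of diameters since treatment started including the baseline sum of diameters" (Table 2). A TL meets CR at 0 mm, or below 10 mm for a node. A patient has at most five TLs. About 375 patients are in the mITT, randomised 2:1 (SAP 1.3). The lesion sizes below are hypothetical.

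**The plan's own figure.** In Table 3, lesions 1 to 4 sum to 7.2 + 6.7 + 4.3 + 8.6 = 26.8 cm, and lesion 5 brings the total to 29.3 cm. At follow-up, 7.1 + 6.4 + 4.0 + 8.5 = 26.0 cm. Scaled sum = 26.0/26.8 × 29.3 = 28.4 cm, as stated. One lesion in five is missing, which is within the one-third limit.

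**Check 1: missing lesion after a CR.** At the CR visit a node reads 8 mm and two other TLs read 0 mm, so the sum is 8 mm; take this as the nadir. At the next visit one of the two other TLs is not recorded and the other is still 0 mm.

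| | Node stays 8 mm | Node grows to 12 mm |
|---|---|---|
| Step 1 | no, one TL missing | no, node is not below 10 mm |
| Step 2 | yes: **NE** | no, node no longer meets CR |
| Step 3 | – | 12 − 8 = 4 mm, 4/8 = 50%; 4 mm is below 5 mm, so not PD |
| Step 4 | – | **CR** |
| Missing TL data rule | NE | NE |

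Consequences, taken one at a time:
- *ORR.* By Table 5, a TL CR without non-target progression or a new lesion gives an overall CR or PR. The patient was therefore already a responder at the earlier visit, because this ORR needs no confirmation. If there was PD at that visit, later visits do not count. Investigator ORR cannot change.
- *PFS events.* Neither CR nor NE is an event, and SAP 3.2.1 does not count an NE visit as missed.
- *PFS censoring.* Censoring is at the last evaluable assessment. If this is the last scan, CR censors there and NE censors at the previous evaluable scan. On schedule that is 8 weeks earlier up to week 48, and 12 weeks earlier after that.
- *Confirmed best response.* Confirmation needs a second response at least 4 weeks later. CR at this visit supplies it; NE does not.

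**Check 2: lesions with an intervention.** Let k of n TLs be treated. NE applies when k/n exceeds 1/3:
- n = 1: k = 1 (1.00)
- n = 2: k ≥ 1 (0.50)
- n = 3: k ≥ 2 (0.67)
- n = 4: k ≥ 2 (0.50)
- n = 5: k ≥ 2 (0.40)

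Example above the limit: a single TL is irradiated and reads 0 mm. Step 3 gives CR. The Step 2 note, Table 2 and the Scaling text give NE.

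Example at the limit: three TLs of 30 mm at baseline (the nadir), one irradiated, all now 0 mm. The share is 1/3, so scaling applies: 0/60 × 90 = 0 mm, a 100% fall. Step 3 gives CR. The Scaling text bars CR and so gives PR. Both count as a response, so ORR is the same.

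Size of one changed responder: 375/3 = 125 placebo patients, 1/125 = 0.8 points; 250 durvalumab patients, 1/250 = 0.4 points. ORR uses only patients with measurable disease, so these are minimum values.

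**The case against.** The best defence of Step 3 is that it is a deliberate exception: the treated lesion must have a recorded value, and a recorded 0 is not missing data. That is a fair reading and could be the intended one. The text does not say so. The Step 2 note counts treated lesions as set to missing, and the Scaling paragraph is limited to such lesions, so its bar on CR has nothing else to apply to. Step 3 also ends by giving NE where too few measurements remain for scaling.

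The second defence is that little follows, and most of this stands. Check 1 leaves ORR and PFS events alone. Check 2 changes ORR only if more than one third of TLs were treated, all read 0 mm (below 10 mm for nodes), and there was no earlier response, no earlier progression and no counted subsequent therapy. Radiotherapy for cancer during study treatment is prohibited (Protocol 6.4, Table 5). The case therefore arises mainly after discontinuation, when scanning continues (Protocol 7.1.1) and palliative radiotherapy does not count as subsequent therapy.

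Third, SAP 3.1.1.1 refers to Protocol Appendix E for special cases of TLs. Appendix E is not in the text I worked from, and it may state a precedence.

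A reader might also infer that the nadir rules conflict and turn PD into SD. Under Missing TL data, "the nadir can only be taken from assessments where all the TLs had an LD recorded"; under Scaling, "the scaled-up sum of TLs diameters will be included when defining the nadir value for the assessment of progression". The documents do not support that reading. Take TLs of 30/30/30 mm; visit 1 is 20/20 with the third irradiated and not recorded; visit 2 is 25/25 with the third missing.
- Under the Scaling rule, the nadir is 40/60 × 90 = 60 and visit 2 is 50/40 × 60 = 75. That is +25% and +15 mm, so PD.
- Under the missing-data rule alone nothing is scaled. The available 50 mm against 90 mm is not PD, so the visit is NE.

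SD appears only if visit 2 is scaled under one rule and compared with the nadir of the other (75 against 90, −17%). The intervention text says expressly that treated lesions are scaled when the nadir is found. It is a special rule beside a general one, and only its wording is loose.

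**Conclusion.** Both inconsistencies are in the current text, and both are minor. After a CR, a visit with a missing TL and regrowth short of PD is CR by Step 4 and NE by the missing-data rule. This can move an Investigator PFS censoring date by one scan interval, or make or remove a confirmed Investigator best response, and no more. With more than one third of TLs treated and all at 0 mm (below 10 mm for nodes), the visit is CR or NE. This can change Investigator ORR, by at least 0.8 points per placebo patient or 0.4 points per durvalumab patient. At one third or fewer it is CR or PR, and ORR does not change.

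A reader might extend this to the primary PFS, but SAP 3.1.2 says that the central reviewers supply the visit response and that no programmed derivation is needed. SAP 3.1 also says that derivations will be programmed for the BICR. I read that as the endpoints calculated from visit responses, and the conclusion rests on that reading. It also assumes that Appendix E sets no precedence. The documents give no basis for estimating how many visits are affected.

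**What to change.** 1. Limit Step 4 of the post-CR rules to visits where every TL is recorded. With any TL missing and PD not met, set NE.
2. State one order of precedence between the CR sentence in Step 3 of the intervention rules and the one-third and no-CR rules. One way is to restrict or remove that sentence, so that a locally treated lesion cannot produce a CR. Declaring it an exception would also remove the ambiguity, but would leave such responses in the Investigator ORR.
3. As wording only: in the Scaling sentence on the nadir, describe the lesions as missing because of intervention. Under Missing TL data, add that the intervention and Scaling rules govern the nadir for treated lesions.

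The cost is a few sentences in the SAP and matching changes to the Investigator derivation code, made before the Investigator responses are derived. If the CR sentence is removed, an occasional CR after local treatment becomes NE, or PR at one third or fewer.
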